### **6.4. Study Termination Status**

Reason for early study termination or study withdrawal will be enumerated and detailed. Study disposition at the time of a report will list those remaining in study follow-up, completed study follow-up, early withdrawal (including deaths).

### **6.5. Demographic and Baseline Characteristics**

#### **6.5.1. Demographics and risk characteristics**

The following baseline demographics and risk characteristics will be presented separately by arm for the ITT cohort.

- Age in years
- Education
- Sexual risk (i.e. number of partners, transactional sex, condom use with last sex)
- Living situation
- Preferred language
- Marital status
- Number of live births
- Earns her own income (Y/N)

#### **6.5.2. Baseline Laboratory Data**

Baseline bacterial STI diagnoses (GC/CT, Syphilis) detected by lab-based study testing will be reported for each cohort separately, by arm and by study site.

## 7. EFFICACY

### 7.1. General Considerations

Tabulations will be by study arm, for each quarter of study follow-up (or at visits where evaluated). These will be reported in only the closed report during the study.

Inferential statistical tests will be two-sided and will be performed at alpha levels of 0.05 and 0.10 to declare the significance of main effects and interaction effects, respectively.

### 7.2. Statement of the Null and Alternate Hypotheses

For enrolled women:

- $H_0$ : Use of Doxycycline PEP does not have a differential effect on incidence of GC, CT and syphilis infections compared to the standard of care

$$RR_{\text{any STI}} (\text{Doxo Arm}/\text{SOC Arm}) = 1$$

- $H_A$ : Use of Doxycycline PEP decreases the incidence of GC, CT and syphilis infections compared to the standard of care.

$$RR_{\text{any STI}} (\text{Doxo Arm}/\text{SOC Arm}) \neq 1$$

### 7.3. Subgroup Analyses

Subgroup analysis of the efficacy of the intervention will be conducted for

- Age subgroups ( $\leq/ > 24$ )
- Nulliparous (N/Y)
- Using contraceptives (N/Y)
- Any STI at baseline (N/Y)
- Transactional sex (N/Y)

### 7.4. Multiple Comparisons and Multiplicity

No adjustments are planned for multiple comparisons

### 7.5. Analysis of the Primary Efficacy Endpoint

#### 7.5.1. Primary Efficacy Analysis

The primary analysis of efficacy will be conducted in the ITT cohort

**Endpoint definitions:**

Primary endpoint: **Any incident STI at Month 3, 6, 9 or 12.** Repeat positive tests for the same STI up to 28 days after treatment of an incident infection (the window for the test of care visit) will not be counted as incident infections. Incident infections detected at interim visits more than

28 days after treatment will be treated in the analysis as if they would have been detected at a scheduled visit (months 3, 6, 9 and 12). Therefore, an STI diagnosed at an interim visit outside the treatment window is carried forward to the next scheduled visit. If a participant has more than one positive STI (different bacterial infections) at a scheduled visit it will be counted as one incident “any STI” event for that visit interval. If scheduled visits are missed, infections will be assigned to the next scheduled visit (i.e., the first missed scheduled visit).

Secondary endpoints: **Any GC, Any CT at Month 3, 6, 9 and 12.** The same approach as defined for the primary endpoint will be used, restricted to each specific bacterial infection.

The criteria for an incident syphilis case will include a four-fold increase in non-treponemal titers (e.g., the RPR) and/or a consistent clinical presentation.

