Microbiome testing (vaginal swab) BV testing (vaginal swab) M. genitalium screening and resistance (endocervical swab) Pharyngeal microbiome and resistance (pharyngeal swab) Rectal microbiome and resistance (rectal swab) Rectal CT screening (rectal swab) HSV-2 testing (serum) Y chromosome DNA testing (vaginal swab) S. aureus resistance screening (nasal swab)	Microbiome testing (vaginal swab)		X	X	X	X	X
	BV testing (vaginal swab)	X	X	X	X	X	X
	M. genitalium screening and resistance (endocervical swab)	X	X	X	X	X	X
	Pharyngeal microbiome and resistance (pharyngeal swab)	X					X
	Rectal microbiome and resistance (rectal swab)						X
	Rectal CT screening (rectal swab)						X
	HSV-2 testing (serum)	X					X
	Y chromosome DNA testing (vaginal swab)	X	X	X	X	X	X
	S. aureus resistance screening (nasal swab)	X	X	X	X	X	X

S = screening visit

aintervention arm only

bif clinically indicated

cParticipants diagnosed with an STI will return 2 weeks following treatment for test of cure

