### *Enrollment Visit:*

The enrollment visit will be as soon as the following day after the screening visit and as late as 28 days following the screening visit. Demographic, behavioral, and facilitators/barriers information will be collected at enrollment. Pelvic exam for baseline STI testing and sample storage will be done at enrollment and prevalent STIs will be treated. Full medical review of symptoms and medications, blood testing (up to 20mL of blood drawn), hair sample, and nasal and pharyngeal swabs will be collected at enrollment. Pregnancy testing will be completed for all women at enrollment.

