### *Quarterly visits after enrollment :*

dPEP (intervention) group: Study visits, every 3 months, will include questionnaires, risk reduction counseling, PrEP and dPEP adherence counseling (including dPEP dosing information), pill count and refill, a blood draw (up to 10mL), HIV testing, a hair clipping, a nasal swab, a pharyngeal swab, (rectal swabs at the final visit only), WHO pregnancy check list (with possible urine pregnancy test), and vaginal and endocervical swabs. All participants will receive reimbursement for attending quarterly study visits.

Standard of care (control) group: Study visits, every 3 months, will include questionnaires, risk reduction counseling, PrEP adherence counseling, a blood draw (up to 10mL), HIV testing, a hair clipping, a nasal swab, a pharyngeal swab, (rectal swabs at the final visit only), WHO pregnancy check list (with possible urine pregnancy test), and vaginal and endocervical swabs. All participants will receive reimbursement for attending quarterly study visits.

Any participant with a positive STI result will be asked to return two weeks after treatment for a test of cure visit, which will include STI testing.

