### 2.2. Study Endpoints

#### 2.2.1. Primary Efficacy Endpoints

##### Effectiveness of doxycycline

The primary endpoint is assessed using the following STI endpoints at month 3, 6, 9 and 12 visits:

- Documented positive vaginal/cervical GC
- Documented positive vaginal/cervical CT
- Early syphilis infection based on four-fold increase in non-treponemal titers.

The primary trial endpoint is any newly diagnosed STI, defined as any one of the above after the enrollment visit, with the exception of re-diagnosis of the same infection at a test of cure visit within 28 days of first treatment of a baseline or incident infections (which is considered a non-cured infection and re-treated). Any infection newly diagnosed at an interim visit will be counted as a primary endpoint for the subsequent scheduled visit i.e., if a participant is diagnosed with new GC infection at an interim visit 40 days after their 6 month visit, this will be analysed as a primary 9 month endpoint. Endpoints are reviewed by committee, blinded to study arm, and primary endpoints designated in that review.

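### SAP 2.2.1 and 7.5.1 give conflicting rules for excluding persistent infections, so an uncured baseline infection could be counted as a primary endpoint, with bias in an uncertain direction

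*SAP*

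**What the plan says.** SAP 2.2.1 (Primary Efficacy Endpoints) counts any newly diagnosed STI after enrollment, except "re-diagnosis of the same infection at a test of cure visit within 28 days of first treatment of a baseline or incident infections". It treats such a case as not cured and says it is re-treated. It then adds: "Endpoints are reviewed by committee, blinded to study arm, and primary endpoints designated in that review".

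SAP 7.5.1 (Endpoint definitions) states the exclusion again in different terms. What is not counted is "Repeat positive tests for the same STI up to 28 days after treatment of an incident infection". Baseline infections are not named. On diagnoses between scheduled visits, the same paragraph says that "an STI diagnosed at an interim visit outside the treatment window is carried forward to the next scheduled visit". The CT and GC endpoints follow the same approach.

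Baseline infections will exist and will be re-tested inside the disputed window. The protocol's Enrollment Visit text says "prevalent STIs will be treated". Footnote c to the Section 6.0 schedule reads "Participants diagnosed with an STI will return 2 weeks following treatment for test of cure", and the quarterly-visit text says "Any participant with a positive STI result will be asked to return two weeks after treatment for a test of cure visit".

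**The concern.** The two rules define the same primary endpoint but can give different event counts from the same data. Take a woman treated for chlamydia at enrollment who is still positive at her two-week test of cure. Section 2.2.1 excludes her. The exclusion sentence in 7.5.1 does not reach her.

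Section 2.2.1 has a gap of its own, because its 28 days run from the first treatment. An infection still positive at about day 14 and re-treated then has its next test of cure at day 28 or later. Past day 28, a known uncured infection falls outside the exclusion and can count as new.

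The ambiguity also carries into the CT-alone analysis. That analysis informs interim stopping (SAP 4.1) and the 66-woman CT target (SAP 3.3.1). Any miscounted baseline infection would fall entirely in the baseline-STI subgroup of SAP 7.3. The primary model has study arm as its only covariate, so it makes no adjustment for baseline infection.

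**Working it through.** **Rules side by side**

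| | SAP 2.2.1 | SAP 7.5.1 |
|---|---|---|
| Infection treated | baseline or incident | incident only |
| Clock starts at | first treatment | treatment (which one is not stated) |
| Test excluded | at a test of cure visit | any repeat positive |
| Length | 28 days | 28 days |

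They differ in three of four respects. Neither covers an uncured infection first re-tested at Month 3, which is beyond 28 days.

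**The plan's own figure (SAP 3.3.1)**

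- Events = 4(1.96 + 0.842)² / (ln 0.5)² = 65.3, so 66.
- Mean risk = (0.22 + 0.11)/2 = 0.165, and 66/0.165 = 400.
- With 10% loss, 200/0.9 = 222.2, so 223 per arm and N = 446. The plan's figures reproduce.

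**Inputs for the dilution check**

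- Control incidence 22% and a 50% reduction (SAP 3.3.1).
- Women followed per arm: 223 × 0.9 = 200.7, about 201.
- Baseline CT plus GC prevalence from the three cohorts in Protocol Table 3: 12 + 4 = 16%, 29 + 8 = 37%, 26 + 10 = 36%. These are sums that ignore co-infection, and they come from other studies.
- Share *f* of treated baseline infections still positive at test of cure: not in the documents. Assumed 2% to 20%.
- Persistence in the dPEP arm relative to control, *k*: not in the documents. Tried at 1, 0.5, 0.25 and 0.

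**Formula.** The quarterly control risk is q = 1 − 0.78^(1/4) = 0.0602, and half of that (0.0301) under dPEP. Persistent baseline infections are added to the Month 3 interval only. With e = prevalence × f in control and k·e under dPEP, the event proportion summed over four visits is 3q + 1 − (1 − q)(1 − e). The ratio of the two sums is what an independence GEE with arm alone estimates.

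Example (37%, f = 20%, k = 1): e = 0.074. Control is 0.1807 + 1 − 0.9398 × 0.926 = 0.310. dPEP is 0.0903 + 1 − 0.9699 × 0.926 = 0.192. RR = 0.62.

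| Prevalence | f | Extra control events (201·e) | RR, k=1 | k=0.5 | k=0.25 | k=0 |
|---|---|---|---|---|---|---|
| 16% | 2% | 0.6 | 0.507 | 0.500 | 0.497 | 0.494 |
| 16% | 10% | 3.2 | 0.531 | 0.501 | 0.486 | 0.471 |
| 16% | 20% | 6.4 | 0.559 | 0.502 | 0.473 | 0.445 |
| 37% | 2% | 1.5 | 0.515 | 0.500 | 0.493 | 0.486 |
| 37% | 10% | 7.4 | 0.567 | 0.502 | 0.469 | 0.437 |
| 37% | 20% | 14.9 | 0.619 | 0.504 | 0.446 | 0.388 |

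The shift changes sign at about k = 0.5, the planned risk ratio. With higher true incidence the shift shrinks. At 47% a year in control (CT 33% + GC 14%, one Table 3 cohort), k = 1 gives 0.503 (16%, f = 2%) to 0.556 (36%, f = 20%).

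**Power, equal persistence only.** Power = Φ(√(D/4)·|ln ratio| − 1.96). With 44 vs 22 events it is 80%. Adding 4 per arm (48 vs 26, ratio 0.54) gives 75%. Adding 8 per arm (52 vs 30, ratio 0.58) gives 70%. This is a first-event approximation, whereas the primary model uses repeat events.

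**First-treatment clock.** The case needs two successive failures. Taking the same failure share each time, 201 × prevalence × f² is 201 × 0.16 × 0.02² = 0.01 to 201 × 0.37 × 0.10² = 0.7 baseline infections per arm. At f = 20% it would be 3.0. The second positive must also fall after day 28.

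**The case against.** A reader might infer that 7.5.1 would count every uncured baseline infection. The text does not go that far. Section 7.5.1 is silent on baseline repeats and calls the endpoint incident. The protocol's Study visits text classes a test of cure as an interim visit, and 7.5.1 carries interim diagnoses forward only when they fall more than 28 days after treatment, outside the treatment window. Those sentences do not limit treatment to incident infections. A day-14 positive therefore has no clear route into the endpoint. Section 2.2.1 is explicit, and the committee that designates endpoints is blinded to arm. Sensitivity analysis 3 (SAP 7.5.2) drops a repeat of the same organism that has no negative test before it, and so would expose an effect.

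This supports saying could rather than would, but it does not remove the conflict. The only sentence in 7.5.1 that describes the window ties it to an incident infection. The protocol's Endpoint adjudication section points the committee to CDC diagnostic guidelines, and neither document says which exclusion rule binds it. Sensitivity analysis 3 is not the primary analysis.

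A reader might also infer dilution toward 1. That holds only if dPEP-arm persistence, relative to control, exceeds the true risk ratio. dPEP is dispensed from Month 0 and the protocol assumes universal CT susceptibility to doxycycline, so extra clearance in that arm is plausible. The bias could then be nil or could overstate efficacy.

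Finally, it is fair to say that the first-treatment problem is a narrow edge case, and that aligning 7.5.1 with 2.2.1 on baseline infections would resolve the main contradiction.

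**Conclusion.** The conflict is real and lies in the definition of the primary endpoint. Read literally, the exclusion in 7.5.1 leaves out uncured baseline infections that 2.2.1 excludes, so they could be counted. The documents do not establish that they would be.

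Size and direction cannot be fixed, because no cure rate or arm-specific persistence is given. Under the assumed ranges, equal persistence moves the risk ratio from 0.50 to about 0.51-0.62. Halved persistence under dPEP leaves it at about 0.50. Complete clearance under dPEP takes it to between 0.49 and 0.39. At the low end the effect is about one event per arm.

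The first-treatment clock is a secondary fault. For baseline infections it is probably under one case per arm, provided persistence is no more than 10%. The case for correction rests on having one unambiguous primary event count in an open-label trial, not on any particular bias.

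**What to change.** Use one rule in SAP 2.2.1, SAP 7.5.1 and the adjudication instructions. A positive test for the same organism within 28 days of the most recent treatment for it, whether the treated infection was baseline or incident, is not an endpoint unless a negative test came in between. This also settles whether the rule applies only at test of cure visits.

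At minimum, add baseline infections to the 7.5.1 exclusion so that it matches 2.2.1. That removes the main contradiction but leaves the first-treatment clock as it is.

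Keep sensitivity analysis 3. It is the only planned analysis that deals with an uncured infection first re-tested at Month 3, which the single rule does not cover.

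The cost is a short SAP edit before database lock and, if endpoints have already been designated, a check of test of cure positives blinded to arm. The downside is that a few true rapid reinfections may be excluded.

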### **Descriptive analysis**

- The number of participants with any bacterial STI, and with each type of STI, will be summarized at each scheduled visit by arm
- The number of STIs reported by each participant will be summarized at each scheduled visit by arm. Detail of testing and results at interim visits will also be summarized.
- Occurrence and results of test of care visits will be summarized.

### **Statistical analysis**

Comparison of STI incidence by arm will be conducted by estimating the relative risks of any STI over the 3, 6, 9 and 12 month visits using a modified Poisson model fitted using GEE methods to account for repeated observations from each participant, assuming an independent covariance structure, with study arm as the only covariate[1]. The test for significance will be a two-sided alpha = 0.05. 95% confidence intervals will be computed using robust standard errors.

The same analysis will be repeated for the individual STIs.

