### 3.3. Sample Size Considerations

#### 3.3.1. Sample Size Justifications

The study is a 1:1 randomized superiority design, comparing dPEP to standard of care. The primary trial outcome will be the combined incidence of incident *C. trachomatis*, *N. gonorrhoeae*, and syphilis infections, compared between the randomization arms, to mirror the IPERGAY and Doxy PEP approach; analyses will also test CT and NG alone. Sample size was determined using an event driven approach (N = 66). Assuming 10% loss-to-follow-up, incidence of 22% for any STI in the SOC arm and a two-sided alpha of 0.05, a sample size of n=446 (n=223 per arm) has 80% power to detect a 50% reduction in time to first STI, i.e. ~11% in the dPEP arm (n=44 vs. 22 cases).

The trial intends to have sufficient power to detect 50% effectiveness in CT alone, and thus not stop before incident diagnosis of CT has occurred in 66 women (resulting in more than the minimum number of composite events for the endpoint of any STI).

Sample sizes were computed using nQuery for time to first STI within one year of follow-up

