### **5.2.9. Subgroups**

The following subgroups will be defined by baseline characteristics

- Age:  $\leq$  vs  $> 24$  years old at enrollment
- Nulliparous: No previous live births
- Using contraceptives: IUD, implants, DMPA, oral contraceptives
- Any STI at baseline: Any laboratory confirmed diagnosis of GC, CT or incident syphilis during enrollment visit(s).
- Transactional sex: exchanged sex for goods, services, or money in the last 3 months

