### **7.5.3. Analyses of the Primary Efficacy Results while on study drug (Per protocol)**

For the per-protocol analysis, for each cohort the dPEP arm will be restricted to study time prior to the first discontinuation (> 2 weeks) of study drug documented on the study dPEP CRF. The evaluation of the impact of doxycycline on Any STI will use the same model as specified for the primary analysis, but also potentially adjusted for age, baseline STI, baseline and follow-up sexual risk (number of partners, nulliparous, contraceptive use, transactional sex).

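### Baseline STI is measured on every woman but is in neither the primary ITT model nor any ITT sensitivity analysis: a valid choice that gives up a little precision and protection against chance imbalance

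*SAP*

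**What the plan says.** SAP 7.5.1 specifies a modified Poisson GEE over the Month 3, 6, 9 and 12 visits. It uses an independence working structure and robust standard errors, and is fitted "with study arm as the only covariate". The same model is repeated for the individual infections.

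Baseline STI is available for every woman. The protocol's schedule of procedures, its enrollment visit and its STI testing section have CT/NG and syphilis tested at enrollment. SAP 5.2.9 defines any STI at baseline as a subgroup, SAP 7.3 lists it for subgroup analysis, and SAP 6.5.2 tabulates it by arm.

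As an adjuster it appears only in SAP 7.5.3, where the per-protocol model is "potentially adjusted for age, baseline STI, baseline and follow-up sexual risk" and further items. None of the four ITT sensitivity analyses in SAP 7.5.2 adds a baseline covariate. Protocol section 10 allows adjusted analyses if needed, and its example confounders do not include baseline STI. Randomisation uses variable-sized blocks (SAP 3.4), with no stratification factor stated.

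**The concern.** If women infected at enrollment are more likely to have an STI in follow-up, leaving baseline status out of the model costs precision. A chance difference between the arms also passes straight into the headline RR.

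That baseline STI is prognostic is an inference, because the documents report no association. Two features of the SAP fit it:
- SAP 7.5.3 names baseline STI as a candidate adjuster.
- The exclusion of repeat positives runs only to 28 days after treatment, so a baseline infection still detectable later could count as incident at Month 3. Sensitivity analysis 3 in SAP 7.5.2 addresses repeat positives without an intervening negative.

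Pre-specification is also at stake. If the arms differ at baseline, the plan contains no fixed adjusted ITT estimate, and one added later would look data-driven. In addition, the per-protocol model may carry covariates that the ITT model lacks. A difference between the two results could then reflect either drug discontinuation or the covariates.

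**Working it through.** **1. The plan's own figures (SAP 3.3.1).** The inputs are 22% annual STI incidence under standard of care, 10% dropout and a 5% two-sided test. The stated result: "a sample size of n=446 (n=223 per arm) has 80% power to detect a 50% reduction in time to first STI".
- Events (Schoenfeld): 4(1.960 + 0.842)² / (ln 0.5)² = 31.4 / 0.480 = 65.4, rounded up to 66.
- Power with 66 events: Φ(√66 × 0.693 / 2 − 1.960) = Φ(0.856) = 80.4%.
- Per arm: 66 / (0.22 + 0.11) = 200, and 200 / 0.90 = 222.2, rounded up to 223, so N = 446.

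The stated 80% power is reproduced with no covariate, so the design does not depend on adjustment.

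**2. Baseline prevalence (protocol Table 3).** CT and NG prevalences are 12% and 4%, 29% and 8%, and 26% and 10% in the three cohorts. With no overlap the sums are 16%, 37% and 36%. If the two infections are independent, the lowest cohort gives 1 − 0.88 × 0.96 = 15.5%. Syphilis was below 2%. A range of about 15% to 37% is therefore reasonable.

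**3. Does adjustment change what is estimated?** No. The Poisson score equations make fitted and observed event totals agree within each arm. Randomisation gives both arms the same expected baseline distribution, so the baseline term cancels in the ratio and the arm coefficient remains the marginal RR. This assumes that missed visits are unrelated to arm and baseline status.

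**4. Precision and power.** The SAP 7.5.1 model was simulated with 223 women per arm, four visits, 10% random dropout, 22% annual risk in controls and true RR 0.5. Assumptions not in the documents are a between-woman frailty variance of 0.5 and the prognostic RR (baseline-positive vs baseline-negative women). Each row below rests on 6,000 trials.

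| Baseline prevalence | Prognostic RR | Power, arm only | Power, arm + baseline STI | Fall in variance of log RR |
|---|---|---|---|---|
| 15% | 2 | 81.9% | 82.6% | 1.6% |
| 30% | 2 | 81.2% | 82.2% | 1.7% |
| 36% | 2 | 81.3% | 82.1% | 1.7% |
| 15% | 3 | 80.2% | 82.2% | 3.8% |
| 30% | 3 | 80.3% | 82.2% | 4.4% |
| 36% | 3 | 80.0% | 81.8% | 3.5% |

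Across all runs (4,000 to 6,000 trials per scenario), the fall was 0-2% at prognostic RR 2, and there was no power difference at RR 1 or 1.5. Mean RR was 0.49-0.50 under both models. With a true RR of 1, type I error was 4.3% to 5.6% for both.

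At a 50% annual rate the variance falls 3-5% (prognostic RR 2) or about 11% (RR 3), but power exceeds 99% either way.

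**5. Chance imbalance.** The SD of the between-arm difference in baseline prevalence p is √(2p(1 − p)/223), which is 3.4 points at p = 15%, 4.3 at 30% and 4.5 at 36%. For a difference d and prognostic RR R, the unadjusted RR is multiplied by [1 + (p + d/2)(R − 1)] / [1 + (p − d/2)(R − 1)].

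| Prognostic RR | 1 SD, p = 15% | 1 SD, p = 30% | 1 SD, p = 36% |
|---|---|---|---|
| 2 | 3.0% | 3.4% | 3.4% |
| 3 | 5.3% | 5.6% | 5.4% |
| 4 | 7.2% | 7.1% | 6.8% |

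At the 95% limit (6.6 points at 15% prevalence, 8.5 at 30%) the shift is about 6-7% for prognostic RR 2 and 11% for RR 3.

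**6. Yardstick.** With 44 vs 22 events, SE(log RR) ≈ √(1/44 + 1/22) = 0.26. The 1 SD shifts above, 3.0% to 7.2%, are 0.030 to 0.070 on the log scale, or roughly 0.11 to 0.27 of one SE.

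**The case against.** The strongest reply is that an arm-only ITT model is a legitimate pre-specified choice. Randomisation removes systematic confounding and the robust interval already allows for chance imbalance. This stands. A reader might infer that the primary RR is biased or the test invalid, but neither the theory nor the simulation supports that.

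A reader might also infer that the SAP contradicts itself by adjusting the per-protocol model and not the primary one. It does not. SAP 7.5.3 makes the adjustment optional. That analysis also truncates only the dPEP arm at discontinuation, which can create confounding that the ITT comparison does not have.

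The tabulation by arm (SAP 6.5.2), the subgroup estimates (SAP 7.3) and the protocol's adjusted analyses if needed offer partial cover. They make an imbalance visible, but none gives a pre-specified adjusted ITT estimate.

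Timing is the most serious practical objection. The SAP's revision log shows changes after the two-thirds interim review and again near the end of data collection, the trial is open-label, and the interim boundaries use p-values from the efficacy analyses (SAP 4.1). Changing the primary model late could make the final test differ from the interim ones and invite suspicion. This limits the form of the fix but does not remove the case for it: SAP section 1 allows revision until database lock, and the protocol restricts closed STI reports by arm to the DSMB and the unblinded biostatistician.

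**Conclusion.** The omission is real and small. The planned analysis is valid, and adding baseline STI changes neither the estimand nor the type I error. At the planned 22% rate the gain is about 0-2% in variance at a prognostic RR of 2 and 3-4% at RR 3, or 0-2 points of power. A 1 SD imbalance shifts the unadjusted RR by about 3-7% over prognostic RRs of 2-4, at most about a quarter of its standard error. The more useful benefit is a fixed adjusted ITT estimate on record if the arms turn out to differ.

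All of this assumes that baseline STI is prognostic, that prevalence is about 15-37%, and that the frailty variance is as simulated. If baseline STI is not prognostic, nothing is gained and nothing is lost. A reader might infer a saving of around 30 women (7% of 446 = 31), but a 7% fall in variance needs a prognostic RR of 4, and nothing in the documents supports a value that high.

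**What to change.** Pre-specify baseline STI (yes/no, as defined in SAP 5.2.9) as a covariate with arm in the ITT modified Poisson GEE.
- If the change can be documented as made before database lock and without access to by-arm results, make this the primary model in SAP 7.5.1 and keep the arm-only model as a sensitivity analysis.
- Otherwise leave the arm-only model primary and add the adjusted model as a named ITT supportive analysis in SAP 7.5.2.

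In SAP 7.5.3, replace the optional adjustment with a fixed covariate list. Adding visit to the model is optional and not needed for this point.

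The cost is a line or two of SAP text, a dated entry in the revision log and no new data. The drawback of the first option is that the final primary model may differ from the one used at the interim looks. The supportive-analysis option avoids this.

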## **4. PLANNED ANALYSES**

### **4.1. Interim Analyses**

The trial will be monitored by an independent data monitoring committee approximately every 6 months. The trial plans to continue until we have established definitive efficacy results, whether effective or ineffective, for both CT alone and for any STI. Two formal interim monitoring times are planned, when 1/3 and 2/3 of the follow-up visits have been completed, with stopping rules based on consideration of both the primary outcome and the CT outcome alone. Because the outcomes are highly correlated, no adjustment for multiple comparisons is planned. O'Brien-Fleming boundaries will be used, with stopping based on the alpha spending corresponding to observed p-values in the efficacy analyses. Stopping for both efficacy and lack of efficacy will be considered; however, a decision to stop for efficacy will need to balance the need for evidence assessing the potential harm of acquired tetracycline resistance.

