### **4.2. Final Analyses**

The final analysis will be conducted after database lock of all final (12 month) study visits.

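### SAP 7.5.1 tests any STI at two-sided 0.05 with an ordinary 95% CI and does not tie that level to the O'Brien-Fleming efficacy looks in SAP 4.1

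*SAP*

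**What the plan says.** SAP 4.1 (Interim Analyses) plans two formal looks, when 1/3 and 2/3 of follow-up visits are complete, and allows stopping for efficacy. On the boundary it says: "O'Brien-Fleming boundaries will be used, with stopping based on the alpha spending corresponding to observed p-values in the efficacy analyses". It gives no total alpha, spending formula, interim critical values or final critical value. It adds that "a decision to stop for efficacy will need to balance the need for evidence assessing the potential harm of acquired tetracycline resistance", so an efficacy stop is a judgement and not automatic.

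SAP 7.5.1 gives the rule for the primary comparison: "The test for significance will be a two-sided alpha = 0.05. 95% confidence intervals will be computed using robust standard errors". It does not mention 4.1. SAP 7.1 repeats the level: "Inferential statistical tests will be two-sided and will be performed at alpha levels of 0.05 and 0.10", for main effects and interactions respectively. SAP 3.3.1 uses the same figure for design: "Assuming 10% loss-to-follow-up, incidence of 22% for any STI in the SOC arm and a two-sided alpha of 0.05".

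SAP 4.2 adds: "The final analysis will be conducted after database lock of all final (12 month) study visits". Protocol section 6.0 (DSMB) refers to pre-specified efficacy and futility rules at the two looks and to monitoring guidelines to be discussed before the trial starts, but gives no numbers. SAP 10 shows that version 3.0 followed the DSMB review at the 2/3 look and that version 4.0 came later. SAP 1 says the final SAP is to be filed before database lock.

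**The concern.** Alpha spent at a look is not available at the end. With two O'Brien-Fleming looks and an overall two-sided level of 0.05, the last analysis must use a cut-off slightly below 0.05. SAP 4.1 and SAP 7.5.1 therefore give different answers when the final p is just under 0.05: 7.5.1 as written declares significance, and the boundary implied by 4.1 does not. Section 7.5.1 is the one an analyst will carry out. At stake is the decision rule for the primary endpoint, within a narrow band of p-values, and the confidence level attached to the relative risk.

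**Working it through.** **The plan's own figure first.** The design (SAP 3.3.1) is 66 events and 446 women for 80% power against a 50% reduction at two-sided 0.05. By Schoenfeld's formula, events = 4(1.960 + 0.842)² / (ln 0.5)² = 4 × 7.85 / 0.480 = 65.3, so 66. Power at 66 is Φ(√66/2 × ln 2 − 1.960) = Φ(2.816 − 1.960) = 80.4%. Average incidence is (22% + 11%)/2 = 16.5%; 66/0.165 = 400; 400/0.9 = 444.4, or 223 per arm and 446 in all. The figures reproduce, using fixed-sample formulas with no allowance for interim looks.

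**Inputs for the error calculation.** Looks at 1/3 and 2/3 (SAP 4.1); last test at |Z| > 1.960 (SAP 7.5.1). Assumed: visit fraction equals information fraction, futility stopping is non-binding, and a crossing at a look counts as a claim.

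**Boundaries.** The SAP does not say which O'Brien-Fleming version applies, so three are shown:
- A: Lan-DeMets with 0.025 per side, cumulative two-sided spend 4[1 − Φ(2.241/√t)].
- B: classical, critical value c/√t with c chosen so that the total is 0.05.
- C: Lan-DeMets on the two-sided total, cumulative spend 2[1 − Φ(1.960/√t)].

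Critical values come from recursive numerical integration of the two-sided process.

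| Version | Z at 1/3, 2/3, end | Spent after two looks | Final p boundary | Error if last test uses 1.960 |
|---|---|---|---|---|
| A | 3.710, 2.511, 1.993 | 0.0121 | 0.0463 | 0.0121 + 0.0414 = 5.35% |
| B | 3.471, 2.454, 2.004 | 0.0143 | 0.0451 | 0.0143 + 0.0403 = 5.46% |
| C | 3.395, 2.407, 2.015 | 0.0164 | 0.0439 | 0.0164 + 0.0392 = 5.56% |

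In the last column the second term is the chance of no crossing at either look followed by |Z| > 1.960 at the end. A 20-million-path simulation gave 5.35%, 5.45% and 5.55%. The matching CI levels are 1 − 0.0463 = 95.4%, 1 − 0.0451 = 95.5% and 1 − 0.0439 = 95.6%.

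**Sensitivity.**
- Timing: with the first look at 0.25-0.40 of information and the second at 0.60-0.75 (assumed), error over all three versions is 5.23-5.74% and the final p boundary is 0.0414-0.0476. A later second look raises it further: at 0.33 and 0.80, version C gives 5.81%.
- Which looks count: if only the 2/3 look can support a claim, error is 5.35%, 5.44% or 5.54%. If neither can, it is 5.00%.

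**Power.** At the drift that gives 80% in a fixed design (2.802), replacing 1.960 by the proper final boundary changes power from 80.4% to 79.5% (A), 80.5% to 79.3% (B) and 80.6% to 79.1% (C): losses of 0.9, 1.2 and 1.4 points. Over the timing range the loss is 0.6-2.0 points.

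**The case against.** The best reply is that 0.05 is the overall level. Alpha spending needs a total, and 0.05 is the only main-effect alpha in the SAP (3.3.1, 7.1, 7.5.1). SAP 7.5.1 does not call 0.05 the last-look cut-off, and a per-analysis 0.05 would also apply at the looks, which contradicts 4.1. On that reading 4.1 governs how 0.05 is spent, and 7.5.1 merely lacks a cross-reference. This is plausible, and it rules out saying that the plan chose an inflated error rate. It does not remove the point: nothing in either document states the reading or links the two sections, and 7.5.1 gives a concrete rule that exceeds 5% if followed after the looks.

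The spending function may also be recorded in DSMB guidelines that are not in these documents. That affects where the missing detail comes from, but the final test still has to be set in the SAP.

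Efficacy stopping is discretionary under 4.1, so at a given look timing and boundary version the error figures are ceilings. That stands.

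Two further inferences are tempting. One is that the intention in 3.3.1 to "not stop before incident diagnosis of CT has occurred in 66 women" bars a claim at the looks and so keeps the error at 5.00%. The SAP does not say how that sentence ranks against the boundaries in 4.1, or whether a crossing without a stop is a claim, so it cannot be relied on here. It is a separate stopping-rule question. The other is that stopping "with stopping rules based on consideration of both the primary outcome and the CT outcome alone" adds multiplicity to this error. That too is a separate matter; the figures here concern any STI alone.

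**Conclusion.** The point holds as a small, conditional gap that should be closed. SAP 7.5.1 and 4.1 are not tied together, and the overall level and final boundary are unstated. Followed literally, with a crossing at either look counting as a claim, overall two-sided error is 5.35-5.56% at exactly 1/3 and 2/3 of information and about 5.2-5.7% over the assumed timings. It is 5.00% if no look could support a claim. The consequence is confined to a final p between the proper boundary and 0.05; that boundary is about 0.044-0.046 at exactly 1/3 and 2/3.

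A reader might infer that the sponsor planned a test above 5%, or that 5.56% is a hard maximum. The documents support neither. Intent is unclear, and the range depends on the look timing, the boundary version and the non-binding futility assumption.

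**What to change.** Before database lock, amend SAP 7.5.1 as follows:
- State that 0.05 is the overall two-sided level for any STI.
- Name the spending function actually used at the two looks, citing the DSMB guidelines if it is recorded there.
- Declare significance only at the final O'Brien-Fleming boundary, recomputed at the actual information fractions. At exactly 1/3 and 2/3 this is p < 0.0463, 0.0451 or 0.0439 for versions A, B and C.
- Report the relative risk with the matching CI (about 95.4-95.6%), or label the 95% CI as nominal.

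If guidelines written before the looks barred an efficacy claim at both, cite them and keep 0.05 as the final level. Since the 2/3 look has been held, the fractions and boundary used should already be known.

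The cost is SAP wording and about 0.9-1.4 points of power at looks of 1/3 and 2/3. No new data are needed.
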